# Procotols for preparation of hypnotics

MTcap group: The blister packs containing the hypnotic will be prepared by Lynn Oaks Compounding Pharmacy located in Thousand Oaks, California, which has staff that are experienced in preparing medications for research purposes. [name] will write prescriptions for the appropriate hypnotic that will cover the entire intervention period. The prescriptions will be sent via encrypted email or fax to the pharmacy. The compounding pharmacy will prepare the blister packs for the intervention period (e.g., 8 weeks, but could be longer if the participant needs a prolonged taper) and send them via overnight mail or courier to the VA Research Pharmacy. If necessary, the medications will be picked up by research staff and transported to the Research Pharmacy. The research pharmacist will label the blister packs per VA protocols. The prescription will be entered into CPRS as a non-VA prescription.

SGT+CBTI group: [name] will write prescriptions for the appropriate hypnotic that will cover the entire intervention period. The prescriptions will be sent via encrypted email or fax to the pharmacy. The compounding pharmacy will prepare a 30-day supply of the appropriate medication for the participant. The medication will be dispensed in a regular prescription bottle and labeled by the pharmacy. At the end of the month, a second 30-day supply of medication will be prepared and dispensed. The medication will be sent via overnight mail or courier to the VA Research Pharmacy. If necessary, the medications will be picked up by research staff and transported to the Research Pharmacy. The prescription will be entered into CPRS as a non-VA prescription.

## Protocols for distribution of hypnotics

For both groups, a member of the research team will pick-up the medication bottle or blister packs from the VA Research Pharmacy and give it to the participant at the first intervention session. If the participant does not come to the appointment, the medication will be returned to the Research Pharmacy. If the Research Pharmacy is closed (e.g., the pharmacist has left for the day, is at a meeting), the medication will be stored either in a locked safe (located in Building 115, Room 328) or the locked narcotics box in the Clinical Research Center (CRC) in Building 500 on the West Los Angeles campus until the Pharmacy reopens or it can be given to the participant.

For participants seen on the Sepulveda campus, a research team member will transport the medication via personal car to Sepulveda. The medication will be placed in a locked bag and stored in the trunk during transport. The medication will be stored in a locked safe in Building 25/Room A137 until the participant receives it at the first session. If the participant does not come to the appointment, the medication will be returned to the safe.

### Amendment for telehealth option

Medications will be mailed to participants following the same procedures used by the VA pharmacy service. Participants will also have the option of picking up the medication from our research staff at the Sepulveda VA or West Los Angeles Medical Center.

# Care coordination at end of intervention period

Participants in the MTcap group will be told the benzodiazepine dose that they are taking when they complete the intervention (or if they withdraw before the 9-week intervention period). The primary care providers of participants in both groups will be informed of the final medication regimen, so patients can continue to be monitored for withdrawal, if necessary.

At the last session of the intervention, the interventionist will use a debriefing script (see attached Debriefing Script) to inform MTcap participants of the actual doses that they were taking over the 9-week intervention. Participants will be given the taper schedule that the SGT+CBTI group followed (see attached Taper Schedule) unless there was a plateau in the tapering, in which case participants will be shown a revised taper schedule. The interventionist will tell participants the dose that they are currently taking and will review the last week's sleep diary to compare what participants thought they were taking with the actual dose. Participants will be given an opportunity to ask questions about the research, will be asked if they agree to allow the investigator to use the data collected up to that point in the study (additional data will be collected at post-treatment, and 6-months), and will be given contact information for the interventionist and [name].

# Follow-up assessments

We will encourage participants to complete assessments even if they elect not to complete the intervention. All follow-up assessments will be conducted by research staff who are blinded to group assignment.

#### Post-treatment assessment

The post-treatment assessment will begin on the same day that the participant completes session 8 of either intervention. At the end of session 8, a participant will be provided with an actigraph to wear at home for 1 week and a sleep and medication diary to complete. When the participant returns the actigraph and diary after 1 week, he/she will be administered selected questionnaires included in the baseline assessment. In addition, a urine sample will be collected to confirm participants' self-report of hypnotic discontinuation. Participants will also be given a six-month fall log to record any falls they experience during the period between the post-assessment and the six-month follow-up assessment. The CURES database will also be queried to obtain data about prescriptions for controlled medications. Participants who complete the post-treatment assessment will receive \$50 for their travel and time.

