| Alcohol, Smoking and Substance
Involvement Screening Test
(ASSIST)         | Standard                      | Screens for substance abuse   |   |                                |      |          |  |
| Trails A & B tests   | Standard                      | Mental processing speed, attention, executive functioning   | Х |                                | Х    | Х        |  |
| Digit Symbol Substitution and Symbol Copy                                        | Standard                      | Mental processing speed and attention   | Х |                                | Х    | Х        |  |
| Mini-Mental State Examination (MMSE)   | Standard                      | Cognitive status  | Х |                                | Х    | Х        |  |
| One-leg standing balance   | Standard                      | Balance measurement   | Х |                                | Х    | Х        |  |
| Benzodiazepine Dependence Questionnaire (DBEP)35  | Standard                      | Symptoms of benzodiazepine dependence   | Х |                                | Х    | Х        |  |
| Clinical Institute Withdrawal
Assessment Scale –
Benzodiazepines (CIWA-B)  | Standard                      | Symptoms of benzodiazepine withdrawal   | x | x                              | х    | х        |  |
| Credibility/expectancy
questionnaire (CEQ)                                    | Standard                      | Self-reported confidence in treatment   | × | Х                              | X    | ×        |  |
| Demographic questions   | Study-specific (attached)     | Characteristics of participants (e.g., marital status, living location, employment)   | х |                                |      |          |  |

| Fall event question                  | Study-specific (attached) | History of slips/trips/falls   | Х |   | Х | Х |
|--------------------------------------|---------------------------|--|---|---|---|---|
| ICSD-3 questions                     | Study-specific (attached) | Symptoms of insomnia based on ICSD-3 criteria  | Х |   | Х | Х |
| Additional comorbidity questions     | Study-specific (attached) | Self-reported medical/psychological conditions                                       |   |   |   |   |
| Nighttime urinary symptoms questions | Study-specific (attached) | Frequency and impact of nighttime urination  | Х |   | Х | Х |

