| Hypnotic abstraction form            | Study-specific (attached) | Prior and current use of hypnotics   |   |   | Х | Х |
| Medication log                       | Study-specific (attached) | Medications taken during week while wearing wrist actigraph                          | Х |   | Х | Х |
| Sleep diary                          | Study-specific (attached) | Self-reported daily sleep patterns   | Х | Х | Х | Х |
| Fall log                             | Study-specific (attached) | Self-reported daily fall record  |   |   | Х | Х |
| Treatment arm question               | Study-specific (attached) | Self-reported question asking participant which treatment received                   |   |   |   | х |
| Watch-PAT instruction sheet          | Study-specific (attached) | Questions about sleep apnea
device use and times
associated with Watch-PAT use | Х |   |   |   |
| Subject Contact Information sheet    | Study-specific (attached) | Updated contact information  |   |   | Х |   |

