# Amendment for telehealth option

Post-treatment follow-up assessment (begins at end of session 8)

Prior to intervention session 8 VVC visit, participants will receive by mail/pick-up the following items:

- Wrist actigraph
- Sleep diary
- Questionnaire packet
- Medication log
- Fall log
- Postage-paid return, insured Return Box to return the study materials (e.g.,actigraph)

Participants will also be instructed to go to the VA clinical laboratory to provide a urine sample.

At the end of session 8, the participant will be instructed to put on the actigraph to wear at home for 1 week and to complete the sleep and medication diary each day of that week.

One week later, a VVC post-treatment assessment visit will occur. At that visit, the participant will be administered selected questionnaires included in the baseline assessment. Participants will also be instructed to record any falls they experience over the next six months in the fall log. Participants will mail/deliver the actigraph and sleep diary back to the study office.

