# Amendment for telehealth option

If a participant needs clinical evaluation during a VVC appointment, staff will advise the participant to seek medical care locally at the nearest emergency department, or for life-threatening emergencies, we will call 911.

- Confusion about duplicate hypnotic prescriptions: Participants may not understand that the hypnotic provided by the study (in blister packs or medication bottle) replaces the hypnotic that they were previously taking. This could result in participants taking both prescriptions at the same time, which would result in a higher dose than prescribed, and possible side-effects (e.g., daytime sleepiness, dizziness). To avoid confusion about duplicate hypnotic prescriptions, participants in both groups will be asked to bring all their medications to the first intervention session. The interventionist will identify the hypnotic that will be tapered and will place the bottle in a sealed envelope. A label will be affixed to the outside of the envelope that states, "Do not take this medication during the 8-week SWITCH study unless instructed by the study staff." The interventionist will explain that the participant will receive the same hypnotic either in a new medication bottle or in the blister packs and should put the old prescription in the sealed envelope in a safe location.
- Increased daytime sleepiness: Adjustments to the participant's sleep habits may result in some initial
  daytime sleepiness. Daytime sleepiness will be monitored during each weekly in-person intervention
  assessment with the Epworth Sleepiness Scale, and participants with increased daytime sleepiness will be
  counseled on the possibility of impaired cognition and increased fall and motor vehicle crash risk. If
  excessive daytime sleepiness is thought to be due to study-related sleep restriction (as opposed to, for
  example, a newly-prescribed medication from the individual's physician), the prescribed sleep schedule will
  be adjusted.
- Mental discomfort: The minor risks associated with completion of the questionnaires include tediousness, fatigue, and/or mental discomfort answering the items. Participants could also find wearing the actigraph

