### Amendment for telehealth option

Video/telehealth Standard Practices

VA Video Connect (VVC) will be the preferred platform that will be used for video interactions with research participants. In the event that VVC fails, we will follow current VA guidance and use currently approved patient-facing platforms.

We will use standard video/telehealth practices including verifying the participant's identity, inquiring whether they have privacy during the visit, as well as obtaining their location and an emergency contact, in case of an emergency during the visit.

Our overall procedure for monitoring and reporting study-related adverse events includes:

Step 1: If a participant reports or monitoring reveals a study-related adverse event, research staff will report this to the Principal Investigator ([name]). When [name] is unavailable, [name] (study co-investigator) will be contacted. The research staff will closely adhere to VAGLA emergency reporting policies and procedures.

- Step 2: If indicated, [name] will speak with the participant to determine the severity and likely cause of the concern. If medical examination is needed and the situation is non-emergent, the participant will be advised to go to the VA outpatient clinic.
- Step 3: [name] will report the event to the IRB and will make a determination whether study protocols should be modified for that participant, whether the participant should be withdrawn from the study, or whether the study protocols should be modified overall.
- Step 4: All concerns reported by research staff will be documented, whether they appear to be study-related, and will be reviewed monthly by [name].
- If a participant reports a high level of mental distress, or discloses suicidal ideation during the interview process, research staff will follow these steps:
- Step 1: Research staff will immediately contact [name] (or another immediately available clinician) who will do an assessment. If relevant, the participant will be provided with the telephone number for the VHA suicide prevention hotline or other local suicide prevention resources.
- Step 2: If needed, the participant will be taken by research staff to the mental health or primary care outpatient clinic for evaluation and/or treatment. For all life-threatening emergencies at our facility, we call 911 and notify VA police.

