# Exploratory Analysis Plan (E1)

We will describe the frequency of falls in each arm. We will test whether MTcap is associated with not falling, using logistic regression (dependent variable [DV] is fall [binary]), which will be predicted as a function of treatment group assignment. E2: Mediation analyses to elucidate the relationship between insomnia severity, hypnotic use, and balance will be conducted using a statistical macro developed by UCLA, which simultaneously tests for the associations of the independent variable (IV; ISI) on the DV (balance), IV on the mediator (hypnotic dose in diazepam equivalents), and IV (ISI) plus mediator (hypnotic dose) on DV (balance) (Sobel, Goodman, and Goodman II tests). Similar mediation analyses (using a Stata user written command for binary mediation) will be performed for the DV, history of fall.

Amendment: We will conduct the same analyses above, but with the addition of data from participants recruited and seen at the UCLA Health site. These data will be transferred in a limited data set from UCLA Health to VA Greater Los Angeles under an approved data use agreement.

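### Falls are not asked about or logged on any schedule during the taper, although the protocol warns of fall risk in that period, and the exploratory falls analysis names neither its data source nor its time window

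*Combined protocol and SAP*

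**What the plan says.** **When the log runs.** For in-person participants the Post-treatment assessment section reads: "Participants will also be given a six-month fall log to record any falls they experience during the period between the post-assessment and" the six-month visit. The telehealth amendment to the follow-up assessments mails the log before session 8. The instruction to use it comes at the video visit one week later and looks forward: "Participants will also be instructed to record any falls they experience over the next six months in the fall log". Table 2 describes the log as a "Self-reported daily fall record" and marks it at the post-treatment and six-month points only.

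**The other fall item.** Table 2 also lists a fall event question ("History of slips/trips/falls") at baseline, post-treatment and six months. Its intervention column is blank, and the main text gives no recall window.

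**The risk named for the treatment period.** Under Potential Risks and Safety Plan, participants with increased daytime sleepiness are to be "counseled on the possibility of impaired cognition and increased fall and motor vehicle crash risk". The same section names dizziness among possible withdrawal symptoms.

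**Reporting.** Step 1 of the adverse event procedure sends a study-related event, whether reported by the participant or found by monitoring, to the Principal Investigator. Step 4 reads: "All concerns reported by research staff will be documented, whether they appear to be study-related, and will be reviewed monthly".

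**Analysis.** E1 states: "We will test whether MTcap is associated with not falling, using logistic regression". The outcome is binary. Neither the instrument nor the period is given.

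**The concern.** Dose reduction and sleep restriction both happen during the intervention, and the protocol itself links that period to a higher chance of falling in some participants. It is also the only period in which one arm tapers masked and the other tapers openly. Yet the one prospective fall instrument is switched on after it has ended.

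Two things are at stake. The first is safety ascertainment. The plan allows the taper or the sleep schedule to be reconsidered during treatment, but none of the listed weekly inputs is a fall report, so a fall that nobody mentions is not available to that decision. The second is the meaning of E1. Without a stated source and period, a reader of the result cannot tell whether falls during tapering were counted or how they were ascertained.

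**Working it through.** The plan gives no figure for this point, so there is none to reproduce. The check has three parts.

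**1. Is any fall item scheduled between session 1 and session 8?**

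| Contact or instrument during treatment | Where described | Fall item? |
|---|---|---|
| Weekly withdrawal assessment: CIWA-B, vital signs, ISI, ESS | Interventions, table footnote; Measures collected during intervention | None listed |
| Daily sleep and habits diary | Telehealth amendment following the measures list | None listed |
| Materials mailed before session 1 | Telehealth amendment to Interventions | No fall log |
| Fall event question | Table 2 | Intervention column blank |
| Daily fall log | Table 2 | Intervention column blank |

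The Interventions table schedules 8 sessions plus 2 withdrawal-only contacts: 8 + 2 = 10 contacts. None has a listed fall question.

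**2. How long is the gap?**

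Inputs:
- T, weeks from session 1 to session 8: about 9 (Interventions).
- Log start: one week after session 8 (Post-treatment assessment, and its telehealth amendment).
- Six-month visit: six months after session 8 (Six-month follow-up), taken as 26 weeks. This conversion is an assumption.

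Formulas: weeks without a log = T + 1; total weeks = T + 26; share = (T + 1)/(T + 26).

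- Planned schedule, T = 9: (9 + 1)/(9 + 26) = 10/35 = 28.6%.
- Weeks covered by the log: 35 − 10 = 25.

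The Extended taper plan allows up to 16 weeks of taper but does not say outright that session 8 moves to the end of it. If it does, the most extreme case is T = 16: (16 + 1)/(16 + 26) = 17/42 = 40.5%. If session 8 stays at week 9, the share remains 10/35. The firm figure is therefore about 29%. The 40% figure is an upper illustration under an unstated assumption.

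**3. What could E1 be measuring?**

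- If the source is the log, falls between session 1 and the post-treatment visit are absent.
- If the source is the post-treatment fall event question, they may be included, but by recall over an unstated window.

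Neither source gives prospective counts of falls during masked versus open tapering.

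**The case against.** The best defence is that participants are seen every week. The Interventions section has progress notes reviewed at weekly intervention meetings, and Step 1 can carry a study-related fall to the Principal Investigator as soon as it is mentioned. The likely precursors are also watched: sleepiness weekly with the ESS, with the sleep schedule adjusted where study sleep restriction is thought responsible, and withdrawal weekly with the CIWA-B and vital signs, with escalation. The fall warning is addressed to sleepier participants rather than to everyone, and the safety plan calls withdrawal symptoms at low doses uncommon. Finally, both arms follow the same dose reduction schedule and the Specific Aims attribute benefit to discontinuing hypnotics, so logging falls afterwards has a rationale. E1 is only exploratory.

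Much of this stands, and it rules out several stronger readings that a reader might infer:

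- *That falls during the taper cannot be seen in time to act.* The weekly contacts, the weekly meetings and Step 1 give a volunteered fall a prompt route.
- *That about four weekly reductions of roughly 25% could pass before a monthly review.* This ignores the weekly meetings. Step 4 also does not say that the monthly review is the first time a physician hears of an event.
- *That E1 uses prospective data leaving out the treatment period.* E1 names no source. The post-treatment fall question could supply falls from that period.

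What the defence does not supply is a scheduled question. Every route during treatment depends on the participant raising the fall unprompted, and Step 1 is framed around events judged study-related. Monitoring sleepiness and withdrawal is not the same as asking about falls.

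**Conclusion.** The concern holds in a limited form. The documents list no scheduled or prospective fall ascertainment during the intervention. About 10 of 35 weeks (29%) have no log on the planned schedule, taking six months as 26 weeks and log issue as one week after session 8, and the gap is longer if session 8 moves with an extended taper. In that window ascertainment is passive (spontaneous report) or retrospective (one question with no stated window).

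E1 leaves source and period open, so a between-arm comparison of falls during tapering would rest on recall or be absent. This bears on safety monitoring and on one exploratory analysis. It does not touch the primary aims or the secondary aim on balance and cognition. It is a cheap improvement worth making, not a flaw that threatens the trial's main conclusions. The fall question is an attached form not available here. If it specifies a window covering the whole intervention, the recall problem narrows, but no prospective record is created.

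**What to change.** 1. Issue the existing fall log at session 1 in both arms. Mark the Intervention column for it in Table 2, and add it to the materials mailed before the first session in the telehealth amendment to Interventions.
2. Have the log checked at each weekly withdrawal assessment, including the two withdrawal-only contacts.
3. State in the adverse event procedure that any fall during the intervention is reported to the Principal Investigator under Step 1, whatever its presumed relation to the study.
4. In E1, name the participant-completed log as the source and report two periods separately: session 1 to post-treatment, and post-treatment to six months.

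Cost: no new form, visit or staff. On the planned schedule the log would run about 35 weeks instead of 25, so participants carry somewhat more diary burden. The weekly check adds a short item to contacts that already take place. Reporting falls regardless of presumed relatedness will produce more event reports to review.
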